4.1.2 Secondary efficacy endpoints

4.1.2.1 Clinical Secondary Endpoints

- Response to treatment with IFN-K, as measured by the SLE Responder Index (SRI)-4 response criteria at Week 36:
 - Reduction \geq 4 points in SELENA-SLEDAI at week 36 compared with baseline
and
 - No new BILAG A at Week 36
and
 - No more than 1 new BILAG B at Week 36
and
 - No deterioration at Week 36 in PGA (< 10% worsening) on VAS 100 mm compared with baseline
- Response to treatment with IFN-K, as measured by the composite SLE Responder Index (SRI)-4 response criteria at Week 36:
 - Same criteria as above
and
 - Sustained reduction in oral corticosteroids (\leq 5 mg and \leq 7.5mg/day) at Week 36 (these criteria will be identified by medical review)
- Response to treatment with IFN-K, as measured by SLEDAI response, defined as a reduction of the SLEDAI-2K score of at least 4 points at Week 36 compared to baseline
- Response to treatment with IFN-K, as measured by BILAG grade changes by body system
- Response to treatment with IFN-K, as measured by Incidence of SLE flare (SELENA SLEDAI flare index. BILAG flares)
- Response to treatment with IFN-K, as measured by SLICC/ACR-DI
- Response to treatment with IFN-K, as measured by Cutaneous LE Disease Area and Severity Index (CLASI)
- Response to treatment with IFN-K, as measured by LLDAS (Franklin *et al*, 2016)

4.1.2.2 Immunogenicity Secondary Endpoints

- Anti-IFN α binding antibody titers
- Anti-IFN α neutralizing antibody titers
- Anti-KLH binding antibody titers

4.1.3 Exploratory efficacy endpoints

- Evaluation of clinical response by assessing disease activity using:
 - PGA scores,
 - number of SLE flares,
 - Time to first SLE flare in patients post randomization,

Statistical Analysis Plan

Study Name: IFN-K-002

SAP version & date: v4, 18/Jun/2018

- 28-Tender and Swollen Joint Counts (SJC),
- Joint Pain VAS
- the incidence of an increase or addition in lupus therapy (intensification and/or add of drugs). (this criterion will be identified by medical review)
- Quality of life using:
 - FACIT fatigue score
 - Changes in the SF-36 score: Physical Component Summary (PCS) and Mental Component Summary (MCS) scores
- Evaluation of biological response by assessing:
 - Changes in the levels of auto-antibodies (ANA, anti-dsDNA, anti-Smith antigen [anti-Sm], anti-RNP, anti-SSA/Ro, anti-SSB/La, anti-cardiolipin, and anti-β2-glycoprotein I antibodies)
 - Changes in levels of biomarkers (C3, C4, CH50)
 - Anti-IFN α and anti-KLH antibody isotyping
 - Neutralizing Anti-IFN α antibodies towards IFN α subtypes
 - IFN β and IFN ω cross neutralization
 - Anti-Hemagglutinin antibody response

4.2 Safety endpoints

The safety and tolerability will be evaluated by the monitoring of the occurrence of AEs and SAEs, clinical laboratory results, physical examinations, vital signs, electrocardiogram and concomitant medications.

4.2.1 Adverse events

Adverse events (AE) will be coded using the MedDRA Version 18 and will be classified by Preferred Term (PT) and System Organ Class (SOC).

A Treatment Emergent Adverse Events (TEAE) will be defined as any adverse event that occurs from the time of first study treatment dose administered to the patient until last study visit.

An SAE is defined as an AE that meets one of the following conditions:

- Death.
- Life threatening event (defined as any AE that places the patient, in the view of the Investigator, at immediate risk of death from the event as it occurred, i.e., it does not include an event that had occurred in a more severe form, might have caused death).
- An event requiring inpatient hospitalization or prolongation of existing hospitalization during the period of protocol defined surveillance.
- Results in a persistent or significant disability/incapacity.
- Congenital anomaly or birth defect in the offspring of a study participant.
- Any other important medical event that may not result in death, be life threatening, or require hospitalization, may be considered a serious adverse experience when, based upon appropriate

Statistical Analysis Plan

Study Name: IFN-K-002

SAP version & date: v4, 18/Jun/2018

medical judgment, the event may jeopardize the patient and may require medical or surgical intervention to prevent one of the outcomes listed above. Examples of such medical events include allergic bronchospasm requiring intensive treatment in an emergency room or at home, blood dyscrasias or convulsions that do not result in inpatient hospitalization, or the development of drug dependency or drug abuse.

Tolerability/safety will be assessed over the 36 weeks study period. The analysis will focus on:

- Occurrence and intensity of any solicited local and systemic reactions during a 7-day follow-up period (i.e. day of study product administration and 6 subsequent days) after each IFN-K or placebo dose
- Occurrence, intensity and relationship of unsolicited AEs occurring throughout the study period
- Occurrence, intensity and relationship of all SAEs occurring throughout the study period
- Rate and severity of viral infections
- Flares (time of occurrence in relation to product administration)

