12.2.2 Diary cards

After each study product administration, patients will be provided with a diary card. These will include the definitions of mild, moderate and severe AEs, as described in Section 12.1.2, in order to facilitate the assessments by the patients of their own level of functional impairment for each experienced AE.

The diary card will be used to record from Day 1 to Day 7 after each immunization, with Day 1 being the day of study product administration, the presence or absence and intensity of the following solicited AEs:

- Local AEs, at each injection site:
 - Pain, itching with grading of intensity.
 - Swelling, redness, induration with measurement of size (in millimeters).
- Systemic AEs:
 - Temperature (°C).
 - Nausea, fatigue, myalgia, headache, with grading of intensity.

Patients will also have the possibility to record unsolicited adverse events.

Patients will be instructed to bring their diary card with them to the unit when they return for their visits. Following discussion of symptoms with the Investigator, information on local tolerability/AEs will be recorded in the eCRF, as appropriate. Diary cards will be retained with the patient's source notes after completion.

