13.4 Safety Endpoints

- Occurrence, intensity and relationship of any solicited local and systemic AEs during a 7-day follow-up period (i.e. day of study product administration and 6 subsequent days) after each IFN-K or placebo dose
- Occurrence, intensity and relationship of unsolicited local and systemic AEs occurring throughout the study period
- Occurrence and relationship of all SAEs occurring throughout the study period
- Occurrence and intensity of solicited local reactions 1 hour post study product administration
- Occurrence and intensity of solicited systemic reactions 1 hour post study product administration
- Hematological and biochemical levels within or outside the normal ranges and percent change from baseline at each visit
- Occurrence, intensity and relationship of any abnormality in physical examination, vital signs, 12-lead ECG, clinical laboratory evaluations
- Rate and severity of viral infections

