5.2.5.2 Adverse events

Adverse event tabulations:

Tabulation of adverse events will present for each cell the following information: number of patients with at least one occurrence of the event, corresponding percentage and number of events (if relevant).

The following tables will be produced for the Safety population as well as by treatment group:

The definition of TEAEs is described in section 4.2.1.

The following period will be defined:

- before first dose
- [1st dose; 2nd dose[
- [2nd dose; 3rd dose[
- [3rd dose; 4th dose[
- [4th dose; 5th dose[
- [5th dose; Week 36]
- [Last dose; Week 36/Early Termination] (for AE which cannot be classified in the previous periods due to dose not received or premature study termination)

Summary table of adverse events (Statistical Table 14.3.2):

- Any AE
- Any TEAE
- Any TEAE by period
- Any TEAE leading to study treatment temporarily discontinuation
- Any TEAE leading to study treatment permanent discontinuation
- Any TEAE of intensity severe or more
- Any TEAE considered related to the study treatment (possibly or probably related)
- Any SAE
- Any SAE by period
- Any Treatment Emergent SAE (TESAE)
- Any TESAE leading to study treatment temporarily discontinuation
- Any TESAE leading to study treatment permanent discontinuation
- Any TESAE considered related to the study treatment (possibly or probably related)
- Any TESAE of intensity severe or more

Statistical Analysis Plan

Study Name: IFN-K-002

SAP version & date: v4, 18/Jun/2018

- Death

Detailed Tables:

All tables listed below will be presented by period (except if otherwise specified):

- Solicited local reactions during a 7-day follow-up period after each study product administration by SOC and PT (Statistical Tables 14.3.3.1 to 14.3.3.6)
- Solicited local reactions during a 7-day follow-up period after each study product administration by SOC, PT and intensity (Statistical Tables 14.3.4.1 to 14.3.4.6)
- Solicited systemic reactions during a 7-day follow-up period after each study product administration by SOC and PT (Statistical Tables 14.3.5.1 to 14.3.5.6)
- Solicited systemic reactions during a 7-day follow-up period after each study product administration by SOC, PT and intensity (Statistical Tables 14.3.6.1 to 14.3.6.6)
- TEAEs by SOC and PT (Statistical Tables 14.3.7.1 to 14.3.7.6)

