- TEAEs by SOC, PT and status of IFN α neutralizing antibodies (positive/negative) at time of event (only on patients IFN-K treated) (Statistical Tables 14.3.7.7 to 14.3.7.10)
- TEAEs by SOC, PT and relationship (Statistical Tables 14.3.8.1 to 14.3.8.6)
- TEAEs by SOC, PT and intensity (Statistical Tables 14.3.9.1 to 14.3.9.6)
- TEAEs leading to permanent study treatment discontinuation by SOC and PT (Statistical Table 14.3.10) (only throughout the study)
- SAEs by SOC and PT (Statistical Tables 14.3.11.1 to 14.3.11.7)
- SAEs by SOC, PT and status of IFN α neutralizing antibodies (positive/negative) at time of event (only on patients IFN-K treated) (Statistical Tables 14.3.11.8 to 14.3.11.11)
- SAEs by SOC, PT and relationship (Statistical Tables 14.3.12.1 to 14.3.12.7)
- SAEs by SOC, PT and intensity (Statistical Tables 14.3.13.1 to 14.3.13.7)
- SAEs leading to permanent study treatment discontinuation by SOC and PT (Statistical Table 14.3.14)

The following rules will be applied to analyze the occurrence of AE according to the status of IFN α neutralizing antibodies (positive/negative):

- For adverse event which occurred between dose 1 and dose 3 included, status of neutralizing capacity will not be assessed
- For adverse event which occurred between 3rd dose (excluded) and Visit 6 (included), status of neutralizing capacity at visit 6 will be used
- For adverse event which occurred between Visit 6 (excluded) and Visit 9 (included), status of neutralizing capacity at visit 9 will be used
- For adverse event which occurred between Visit 9 (excluded) and Visit 12 (included), status of neutralizing capacity at visit 12 will be used

Statistical Analysis Plan

Study Name: IFN-K-002

SAP version & date: v4, 18/Jun/2018

Statistical Analysis Plan

Study Name: IFN-K-002

SAP version & date: v4, 18/Jun/2018

Adverse events listings:

All adverse events (including solicited local and systemic reactions) recorded during the study will be presented in Listings. The following information (if available) will be included in the listings (non-exhaustive list):

- Patient identifier
- Age, Ethnic origin (see section 9 Derived data), gender, weight
- The adverse event (System organ class, preferred term, reported term)
- Start date, end date, duration, period
- Severity (e.g., mild, moderate, severe)
- Seriousness (serious/non-serious)
- Action taken
- Outcome
- Relatedness assessment

Listings will be provided for:

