14.3.5.6	Solicited systemic reactions during a 7-day follow-up period after each study product administration by SOC and PT - Period [Last dose; Week 36/Early Termination]		X			
14.3.6.1	Solicited systemic reactions during a 7-day follow-up period after each study product administration by SOC, PT and intensity - Period [1st dose; 2nd dose[X			
14.3.6.2	Solicited systemic reactions during a 7-day follow-up period after each study product administration by SOC, PT and intensity - Period [2nd dose; 3rd dose[X			
14.3.6.3	Solicited systemic reactions during a 7-day follow-up period after each study product administration by SOC, PT and intensity - Period [3rd dose; 4th dose[X			

Statistical Analysis Plan

Study Name: IFN-K-002

SAP version & date: v4, 18/Jun/2018

Number	Title	Screened	SAF	FAS	PP	Other
14.3.6.4	Solicited systemic reactions during a 7-day follow-up period after each study product administration by SOC, PT and intensity - Period [4th dose; 5th dose[X			
14.3.6.5	Solicited systemic reactions during a 7-day follow-up period after each study product administration by SOC, PT and intensity - Period [5th dose; Week 36]		X			
14.3.6.6	Solicited systemic reactions during a 7-day follow-up period after each study product administration by SOC, PT and intensity - Period [Last dose; Week 36/Early Termination]		X			
14.3.7.1	TEAEs by SOC and PT - Period [1st dose; 2nd dose[X			
14.3.7.2	TEAEs by SOC and PT - Period [2nd dose; 3rd dose[X			
14.3.7.3	TEAEs by SOC and PT - Period [3rd dose; 4th dose[X			
14.3.7.4	TEAEs by SOC and PT - Period [4th dose; 5th dose[X			
14.3.7.5	TEAEs by SOC and PT - Period [5th dose; Week 36]		X			
14.3.7.6	TEAEs by SOC and PT - Period [Last dose; Week 36/Early Termination]		X			
14.3.7.7	TEAEs by SOC, PT and status of anti-IFN α neutralizing antibodies and anti-IFN α binding antibodies at time of event - Period [3rd dose; 4th dose[X			
14.3.7.8	TEAEs by SOC, PT and status of anti-IFN α neutralizing antibodies and anti-IFN α binding antibodies at time of event - Period [4th dose; 5th dose[X			
14.3.7.9	TEAEs by SOC, PT and status of anti-IFN α neutralizing antibodies and anti-IFN α binding antibodies at time of event - Period [5th dose; Week 36]		X			
14.3.7.10	TEAEs by SOC, PT and status of anti-IFN α neutralizing antibodies and anti-IFN α binding antibodies at time of event - Period [Last dose; Week 36/Early Termination]		X			
14.3.8.1	TEAEs by SOC, PT and relationship - Period [1st dose; 2nd dose[X			

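### Unsolicited adverse events are a named safety endpoint, but the SAP's TEAE definition takes in solicited diary reactions and no by-arm table is limited to unsolicited events

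*SAP*

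**What the plan says.** **The endpoint.** Protocol 13.4 lists "Occurrence, intensity and relationship of unsolicited local and systemic AEs occurring throughout the study period" as an item separate from the solicited AEs of the 7 diary days and from SAEs. SAP 4.2.1 keeps the separation: "Occurrence, intensity and relationship of unsolicited AEs occurring throughout the study period".

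**The analysis variable.** SAP 4.2.1 states: "A Treatment Emergent Adverse Events (TEAE) will be defined as any adverse event that occurs from the time of first study treatment dose". The window runs to the last study visit. Solicited reactions are not excluded.

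**Solicited reactions are AEs.** Protocol 12.2.2 has the diary record "the presence or absence and intensity of the following solicited AEs". SAP 5.2.5.2 says: "All adverse events (including solicited local and systemic reactions) recorded during the study will be presented in Listings". SAP 7.3 also refers to the one-hour post-dose reactions as AEs.

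**The outputs (SAP 5.2.5.2 and 10.1).**
- Table 14.3.2 is the overall summary. It has rows for any TEAE, TEAEs by period, severe, related and leading to discontinuation, but no solicited or unsolicited row.
- Tables 14.3.3 to 14.3.6 cover solicited reactions, for example "Solicited local reactions during a 7-day follow-up period after each study product administration by SOC and PT".
- Tables 14.3.7 to 14.3.10 cover TEAEs, starting with "TEAEs by SOC and PT (Statistical Tables 14.3.7.1 to 14.3.7.6". They include breakdowns by neutralizing-antibody status (14.3.7.7 to 14.3.7.10).
- Tables 14.3.11 to 14.3.14 cover SAEs.
- The listings do make the split: solicited local (16.2.7.1), solicited systemic (16.2.7.2) and the remaining AEs (16.2.7.3).

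**The concern.** The endpoint and the variable that is tabulated do not match. A programmer who applies the TEAE definition as written will put every diary reaction into the TEAE tables. The reader of the report then has no by-arm count of patients with an unsolicited AE, a related unsolicited AE or a severe unsolicited AE. A patient listing does not compare the arms.

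This matters because both arms receive an ISA 51 VG emulsion at five visits, each followed by a 7-day diary of ten solicited items. The any-TEAE, related and severe rows are the ones usually cited first, and in them expected injection reactions would be mixed with the events that the unsolicited endpoint is meant to capture. SAP section 7, which lists departures from the protocol, does not mention this.

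**Working it through.** The plan states no figure on this point, so there is none to reproduce. The check sets the table plan against the endpoint, then works out what pooling does to a summary row.

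**Step 1. Classify the numbered AE tables after the summary (SAP 10.1).**

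| Tables | Content | Number |
|---|---|---|
| 14.3.3 to 14.3.6 | solicited only | 4 |
| 14.3.7 to 14.3.10 | TEAEs, no restriction | 4 |
| 14.3.11 to 14.3.14 | SAEs | 4 |
| none | unsolicited only | 0 |

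**Step 2. Which cells are affected.** The solicited items in Protocol 12.1.2 are five local (pain, redness, swelling, itching, induration) and five systemic (fever, headache, fatigue, myalgia, nausea). Under the literal definition the affected cells are:
- the TEAE rows of 14.3.2;
- SOC totals in 14.3.7 to 14.3.10;
- preferred terms that coincide with a solicited item.

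An infection or a malignancy keeps its own uncontaminated preferred-term row.

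**Step 3. Consequences that need no assumed rate.**
- The first TEAE table, "TEAEs by SOC and PT - Period [1st dose; 2nd dose", covers Week 0 to Week 1, that is 7 days with a window of ±1 day (Protocol Table 5). The diary covers Days 1 to 7. This table therefore lies almost wholly inside the solicited window.
- Diary items are graded on the three-grade scales of Protocol Tables 7 and 8. Other AEs use the WHO scale or a four-point scale. The severe row of 14.3.2 and Table 14.3.9 would mix them.
- SAP 4.2.1 assesses solicited reactions on occurrence and intensity only. A pooled Table 14.3.8 would also classify them by relationship.

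**Step 4. Effect on the any-TEAE row.** Let u be the proportion of an arm with an unsolicited AE and s the proportion with a solicited reaction. Assume that the two are independent and that s is the same in both arms.

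P(any TEAE) = 1 − (1 − u)(1 − s)

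Difference between arms = (u₁ − u₀)(1 − s)

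The illustration assumes u = 40% and 60%, a 20-point difference. Neither these rates nor s comes from the documents.

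| s | Any TEAE, arm with u = 40% | Any TEAE, arm with u = 60% | Difference (points) |
|---|---|---|---|
| 10% | 46% | 64% | 18 |
| 30% | 58% | 72% | 14 |
| 50% | 70% | 80% | 10 |
| 70% | 82% | 88% | 6 |
| 90% | 94% | 96% | 2 |

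If s differs between arms, the pooled row can also show a difference that is not in the unsolicited events. With u = 40% in both arms and s = 50% against 70%, it reads 1 − 0.6 × 0.5 = 70% against 1 − 0.6 × 0.3 = 82%.

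**The case against.** **The structure suggests that the TEAE tables were meant to be the unsolicited tables.** The bullets of SAP 4.2.1 match the outputs closely. Solicited reactions (occurrence, intensity) map to 14.3.3 to 14.3.6. Unsolicited AEs (occurrence, relationship, intensity) map to 14.3.7, 14.3.8 and 14.3.9. SAEs map to 14.3.11 to 14.3.13. The listings split the same way, and the sentence that counts solicited reactions among AEs is about listings. This is a fair reading of the intent, but the stated definition contradicts it and nothing else in the SAP overrides that definition.

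**Protocol 13.9.5 asks for all AEs to be summarised by arm.** This stands. A remedy that only removed solicited reactions from the TEAE tables would leave that request unmet, so a combined summary has to stay.

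**The pooling may be slight.** Protocol 5.6 says that few local or systemic reactions were reported in the earlier study, in which 21 patients received IFN-K. On the other side, the Grade 1 thresholds here are low (any redness, swelling or induration above 0 mm; oral temperature from 37.1 °C). Neither fact gives a rate.

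**A reader might infer more than the documents support:**
- That all AE tables rest on TEAEs. They do not: solicited reactions and SAEs have their own tables.
- That unsolicited events vanish from the output. They do not: they are listed, and most keep their own preferred-term rows. Viral infections, severe infections and SAEs are also addressed separately.
- That adjuvant reactions swamp any difference between arms. This would need a high value of s, and none is given. A shared adjuvant also does not make s equal, since one arm adds the conjugate and the other saline.
- That power is lost. The AE analysis is descriptive and plans no test between arms.

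**Conclusion.** The point holds as a mismatch between a named endpoint and its analysis variable. As the SAP is written, unsolicited AEs have no by-arm table for occurrence, intensity or relationship, and the TEAE rows and tables pool them with solicited reactions. This conclusion rests on the text alone.

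The size of the effect does not. In the any-TEAE row an unsolicited difference is multiplied by (1 − s), given independence and equal solicited rates. Under the assumed 20-point difference the row would show anything from 18 points (s = 10%) to 2 points (s = 90%). The documents do not allow a choice within that range.

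The efficacy conclusions are not touched. The change should still be made, because the summary rows cannot be interpreted for this endpoint without it and the split already has to exist for the listings.

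**What to change.** In SAP 4.2.1 and 5.2.5.2:

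1. State that Tables 14.3.7 to 14.3.10, including the neutralizing-antibody tables 14.3.7.7 to 14.3.7.10, and the TEAE rows of Table 14.3.2 cover unsolicited AEs. These are all TEAEs except the diary-solicited terms within the 7-day window after a dose. A solicited term arising outside that window counts as unsolicited. The SAE rows and tables stay as they are.
2. Add a separate row for solicited reactions to Table 14.3.2.
3. Keep a combined all-AE summary to meet Protocol 13.9.5: one any-TEAE row that includes solicited reactions, and one table by SOC and preferred term.
4. Adjust the table titles in SAP 10.1 to match.

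The cost is one flag in the AE dataset, which Listings 16.2.7.1 to 16.2.7.3 need in any case, and a few extra rows or tables. No new data are required.

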4.2.2 Laboratory endpoints

The following clinical laboratory tests are to be performed on collected blood samples:

- Clinical chemistry: Alanine Aminotransferase (ALT), Aspartate Aminotransferase (AST), Alkaline phosphatase, Creatine phosphokinase (CPK), Creatinine, Urea, Total proteins, Albumin, Circulating Anti-Coagulant
- Hematology: Complete blood cell count and differential (RBC, WBC, Lymphocytes, Neutrophils, Platelets); CD19; Total lymphocytes, CD4+, CD8+, Hemoglobin
- Coagulation: INR, Prothrombin time (PT), Partial Thromboplastin Time (PTT), Fibrinogen, Coomb's test (direct)
- Urine: RBC, WBC, Urinary casts, Albumin, Creatinine, Protein concentration, Albumin/Creatinine ratio, Protein/Creatinine ratio
- Dipstick Urinalysis: pH, glucose, etc

Hematology, clinical chemistry, coagulation and urine analysis data will be graded at each scheduled assessment by Modified WHO Toxicity Scale (See Protocol Appendix 10).

Hematological, clinical chemistry and coagulation safety will be based at each visit on raw value, percent change from baseline and categories (grade or normal, Abnormal CS/N, Abnormal CS/AE, Abnormal NCS).

